4.3.3 Participant Registration

Participants who meet eligibility criteria for A5337 will be registered to A5337 according to standard ACTG DMC procedures.

4.4 Coenrollment Guidelines

- A5128, "Plan for Obtaining Informed Consent to Use Stored Human Biological Materials (HBM) for Currently Unspecified Analyses": Coenrollment in A5128 is encouraged and does not require permission from the A5337 protocol chairs.

- A5321, Decay of HIV-1 Reservoirs in Subjects on Long-Term Antiretroviral Therapy: The ACTG HIV Reservoirs Cohort Study, and/or A5322, Long-Term Follow-up of Older HIV-infected Adults in the ACTG: Addressing Issues of Aging, HIV Infection and Inflammation, do not require permission from the A5337 protocol chairs provided that sites can remain within site-specific blood volume limits
- **A5332 (REPRIEVE), Randomized Trial to Prevent Vascular Events in HIV, is allowed as long as participants are not enrolled in any of the REPRIEVE immunology substudies.**
- **A5351s, Effect of Immune-Modulatory Interventions on Cytomegalovirus Replication during Suppressive Antiretroviral Therapy. Coenrollment in A5351s is encouraged and does not require permission from the A5337 protocol chairs.**
- For specific questions and approval for coenrollment in other studies, sites should first check the A5337 PSWP or contact the protocol team via e-mail as described in the Study Management section.

5.0 STUDY TREATMENT

5.1 Regimens, Administration and Duration

Eligible **participants** will be stratified at study entry by class of ART regimen as follows:

Participants taking a non-PI, non-NNRTI containing regimen, and those on a non-PI, RPV-based regimen, will initially receive:

- Sirolimus 0.025 mg/kg/day administered orally once daily with or without food. See Table 2.

Participants taking an NNRTI containing regimen (with the exception of RPV) will initially receive:

- Sirolimus 0.05 mg/kg/day administered orally once daily with or without food. See Table 3.

In order to achieve therapeutic levels, therapy will be initiated with the dosage noted above and dosing will be subsequently adjusted based on trough blood sirolimus concentrations to achieve target concentrations between 5 and 10 ng/mL (see **Table 4**). A detailed dosing table based on the adjustment algorithm in **Table 4** can be found on the A5337 PSWP.

Table 2. Sirolimus Dosing at 0.025mg/kg			
Weight	Initial daily dose	25% increase*	25% reduction*
50 to 70 kg	1.5 mg	2 mg	1 mg
71 to 90 kg	2.0 mg	2.5 mg	1.5 mg
91 to 110 kg**	2.5 mg	3 mg	2.0 mg

*Dose adjustment based on sirolimus trough level.

**For participants weighing >110 kg, the sirolimus dose needs to be clarified by the team.

Table 3. Sirolimus Dosing at 0.05mg/kg			
Weight	Initial daily dose	25% increase*	25% reduction*
50 to 70 kg	3 mg	4 mg	2 mg
71 to 90 kg	4 mg	5 mg	3 mg
91 to 110 kg**	5 mg	6.5 mg	4 mg

*Dose adjustment based on sirolimus trough level

**For participants weighing >110 kg, the sirolimus dose needs to be clarified by the team.

Table 4. Sirolimus Dose Adjustment Algorithm	
Sirolimus level	Dose adjustment*
<5 ng/mL	Increase dose by 25%,
5-10 ng/mL	Continue current dose
>10, <15 ng/mL	Reduce dose by 25%
>15, <20/ng/mL	Hold dose for 48 hours, then decrease dose by 25%
>20/ng/mL	Hold dose until next level check, if <12 ng/mL, then restart study drug at 50% prior dose

*Round dose up to closest sirolimus 0.5mg tablet. Sirolimus tablets cannot be split, crushed or chewed.

Participants will initiate study treatment at week 12 and continue for 20 weeks.

Participants will be followed off-treatment for an additional 12 weeks for a total of 44 weeks. Treatment must be initiated within 72 hours of week 12 (day 0) evaluations (see section 6.2.3).

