5.1 Regimens, Administration and Duration

Participants taking a non-PI, non-NNRTI containing regimen, and those on a non-PI, RPV-based regimen, will initially receive:

- Sirolimus 0.025 mg/kg/day administered orally once daily with or without food. See Table 2.

Participants taking an NNRTI containing regimen (with the exception of RPV) will initially receive:

- Sirolimus 0.05 mg/kg/day administered orally once daily with or without food. See Table 3.

In order to achieve therapeutic levels, therapy will be initiated with the dosage noted above and dosing will be subsequently adjusted based on trough blood sirolimus concentrations to achieve target concentrations between 5 and 10 ng/mL (see Table 4). A detailed dosing table based on the adjustment algorithm in Table 4 can be found on the A5337 PSWP.

NOTE: If there is a change in ART regimen between entry and week 12, the site must contact the A5337 core team ([contact]) as soon as possible to reassess the initial sirolimus dose based on current ART regimen/classification at week 12.

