5.2 Study Product Formulation and Preparation

Sirolimus tablets are obtained from Greenstone LLC. The inactive ingredients include sucrose, lactose, polyethylene glycol 8000, calcium sulfate, microcrystalline cellulose, pharmaceutical glaze, talc, titanium dioxide,

magnesium stearate, povidone, poloxamer 188, polyethylene glycol 20,000, glyceryl monooleate, carnauba wax, di-alpha tocopherol and other ingredients.

Sirolimus tablets 0.5 mg will be provided. These tablets also contain yellow iron (ferric) oxide and brown iron (ferric) oxide. They should be stored at 20° to 25°C [USP Controlled Room Temperature] (68° to 77°F). Dispense in a tight, light-resistant container as defined in the USP.

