6.1.1 Pharmacokinetic Evaluations

See section 6.3.12 for additional details.

Pharmacokinetic (PK) Sampling															
Evaluation	Weeks 12-16										Weeks 18-32				
	Week	12	13	13	14	14	15	15	16	16	18	20	24	28	32
	Day	0	4	7	11	14	18	21	25	28					
Window		±1 day (timed with other study visits as in section 6.1)										±1 week (timed with other study visits as in section 6.1)			
PK Whole Blood Samples for Trough Sirolimus Real-time Monitoring (see section 6.3.12)		X	X	X	X	X	X	X	X	X	X	X	X	X	
Stored Plasma for ARV PK (see section 6.3.12)	X	X		X					X	X		X	X	X	

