6.3.12 Pharmacokinetic Samples

PK Monitoring of Sirolimus

Trough sirolimus levels (whole blood) will be collected 4 days after administration of the first dose of sirolimus and will be analyzed and reported in real time. Trough samples will then be drawn twice a week (approximately days 4 and 7 of each week) for up to 4 weeks until two consecutive drug levels fall within 5-10 ng/mL. Once two consecutive levels fall within 5-10 ng/mL (which may be achieved before the 4-week time point after sirolimus is initiated), trough samples will be drawn every 4 weeks until study week 32 (see section 6.1.1).

The windows for PK sampling are ± 1 day through week 16 and ± 1 week for weeks 18 through 32.

Stored Plasma for PK Exposure Estimates of ARVs

In addition to real-time sirolimus testing, stored plasma will be collected for batched analysis of ARV drug concentrations.

PK Dosing Restrictions

Participants having PK sampling should be instructed to hold their morning doses of sirolimus and ARVs so a trough sample can be collected. Once trough samples have been collected, **participants** can take their normal morning doses of sirolimus and ARVs. For **participants** taking EFV, the evening dose can be taken and the time of the last dose recorded when **participants** come to the clinic for PK blood draws.

PK Data Collection

For sirolimus and ARV PK collection visits, food intake, and date, time and amount of the last three doses of sirolimus and ARVs will be recorded on the CRF.

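### The Table 4 rounding footnote contradicts one or three of the 12 printed adjusted doses, depending on how it is read, and on either reading a 25% reduction ordered at 1.0 mg returns 1.0 mg

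*Protocol*

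**What the plan says.** Protocol section 5.1 sets the starting dose by ART class and weight, then adjusts it to bring the trough to 5–10 ng/mL.

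- **Tables 2 and 3** print, for each of three weight bands, an initial dose, a 25% increase and a 25% reduction. The lightest band reads "50 to 70 kg 1.5 mg 2 mg 1 mg" in Table 2 and "50 to 70 kg 3 mg 4 mg 2 mg" in Table 3.
- **Table 4** gives the rule by trough: below 5 ng/mL, increase by 25%; above 10 and below 15, reduce by 25%; above 15 and below 20, "Hold dose for 48 hours, then decrease dose by 25" per cent; above 20, hold, then restart at half the dose once the level is below 12.
- **Footnote to Table 4:** "Round dose up to closest sirolimus 0.5mg tablet". Tablets may not be split, and section 5.2 states "Sirolimus tablets 0.5 mg will be provided".
- **External table:** "A detailed dosing table based on the adjustment algorithm in Table 4 can be found on the A5337 PSWP". That page is not among the documents. Clarification Memo #1 repeats the reference and leaves the rounding rule as it is.

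Under section 6.3.12, troughs are drawn twice weekly for up to 4 weeks until two consecutive levels are in range. After that, "trough samples will be drawn every 4 weeks until study week 32". The table in section 6.1.1 also lists troughs at weeks 18 and 20.

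**The concern.** A site has two sources for the same step: the printed cell and the footnote. Where they differ, two sites can give different doses for the same trough.

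The more serious case is a reduction ordered because the trough is too high that leaves the dose as it was. The participant stays on the dose that produced the high level, and the next level in the same band orders the same step again. Section 2.1.5 says the risk of interstitial lung disease may rise with the trough, and it attributes the high adverse event prevalence with monotherapy to the lack of drug-level monitoring. Monitoring protects only if the step it triggers changes the dose.

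**Working it through.** **Inputs** (Protocol 5.1, Tables 2–4; 5.2): initial doses 1.5, 2, 2.5, 3, 4 and 5 mg; multipliers 1.25 and 0.75; whole 0.5 mg tablets only.

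**Step 1: the 12 printed cells.** Each exact product is rounded in two ways: always up, and to the nearest 0.5 mg with ties up. Conflicts with the printed dose are in bold.

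| Initial (mg) | Step | Exact | Printed | Always up | Nearest, ties up |
|---|---|---|---|---|---|
| 1.5 | +25% | 1.875 | 2 | 2 | 2 |
| 1.5 | −25% | 1.125 | 1 | **1.5** | 1 |
| 2 | +25% | 2.5 | 2.5 | 2.5 | 2.5 |
| 2 | −25% | 1.5 | 1.5 | 1.5 | 1.5 |
| 2.5 | +25% | 3.125 | 3 | **3.5** | 3 |
| 2.5 | −25% | 1.875 | 2 | 2 | 2 |
| 3 | +25% | 3.75 | 4 | 4 | 4 |
| 3 | −25% | 2.25 | 2 | **2.5** | **2.5** |
| 4 | +25% | 5 | 5 | 5 | 5 |
| 4 | −25% | 3 | 3 | 3 | 3 |
| 5 | +25% | 6.25 | 6.5 | 6.5 | 6.5 |
| 5 | −25% | 3.75 | 4 | 4 | 4 |

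Always up matches 9 of 12. Nearest with ties up matches 11 of 12 and reproduces Table 2 in full. The remaining miss cannot be cured by fixing ties up or down: in Table 3's reduction column the tie at 2.25 is printed downwards (2) and the tie at 3.75 upwards (4). Ties to even fits that column but gives 6 for 6.25, where 6.5 is printed. Nearest with ties down matches 9, and always down matches 7. None of the rules tried reproduces all 12.

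**Step 2: where a 25% reduction changes nothing.**

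- 1.0 × 0.75 = 0.75, which gives 1.0 on both readings.
- 0.5 × 0.75 = 0.375, which gives 0.5 on both readings. Here the tablet strength is the limit.
- 1.5 × 0.75 = 1.125, which gives 1.5 if always up and 1.0 if nearest. Table 2 prints 1 for its 50–70 kg row.

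**Step 3: which ordered reduction is the first to change nothing.** This also depends on whether a printed cell applies wherever that dose occurs or only in its own weight row. The documents do not say.

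| Row (start, mg) | Cells apply across rows, either rounding | Own row only, nearest | Own row only, always up |
|---|---|---|---|
| Table 2, 50–70 kg (1.5) | 2nd, at 1.0 | 2nd, at 1.0 | 2nd, at 1.0 |
| Table 2, 71–90 kg (2) | 3rd, at 1.0 | 3rd, at 1.0 | 2nd, at 1.5 |
| Table 2, 91–110 kg (2.5) | 4th, at 1.0 | 4th, at 1.0 | 3rd, at 1.5 |
| Table 3, 50–70 kg (3) | 4th, at 1.0 | 4th, at 1.0 | 3rd, at 1.5 |
| Table 3, 71–90 kg (4) | 5th, at 1.0 | 6th, at 1.0 | 5th, at 1.5 |
| Table 3, 91–110 kg (5) | 6th, at 1.0 | 7th, at 1.0 | 6th, at 1.5 |

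Only the first row is the same in every column.

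**Step 4: what the hold does.** Section 2.1.8 gives a half-life of 62 ± 16 hours in renal transplant patients; applying it here is an assumption. The fraction left after 48 hours is 0.5^(48/62) = 0.58, and 0.49 to 0.65 for half-lives of 46 to 78 hours. Restarting the same dose then heads back to the same steady state.

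**Step 5: what one tablet fewer at 1.0 mg would do.** The documents do not give the dose–trough relation. Assume that the trough is proportional to dose^e, so that halving the dose multiplies the trough by 0.5^e.

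| e | 10–15 ng/mL becomes | 15–20 ng/mL becomes |
|---|---|---|
| 0.8 | 5.7–8.6 | 8.6–11.5 |
| 1.0 | 5.0–7.5 | 7.5–10.0 |
| 1.2 | 4.4–6.5 | 6.5–8.7 |

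With e = 1.2, starting levels below about 11.5 ng/mL end below the 5 ng/mL target.

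**The case against.** **The web-page table may already settle this.** Tables 2 and 3 print one step each way, and section 5.1 sends sites elsewhere for the detail. A reader might infer that sites did meet a reduction with no effect, or that participants were overexposed. The documents do not show either, and this part of the objection stands. But the web-page table is described as based on the same Table 4 algorithm, so it cannot be assumed to cure the problem.

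**The footnote mostly works.** A reader might infer that it fails for both tables. On the nearest reading it fails for one cell of Table 3, where the dose is printed and no site needs to round. This also stands. The wider conflict, which reaches Table 2, needs the always-up reading.

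**At 1.0 mg the tablet strength is the cause.** With whole 0.5 mg tablets the choice is no change or a 50% cut, and rounding up is a stated rule. This is true, and choosing between them is a clinical judgement. It does not justify calling no change a reduction.

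**Safeguards exist.** Dose changes are keyed within 48 hours (6.3.4). The core team receives summaries of doses and troughs and reviews individual safety data at least monthly (9.5). Toxicity rules act regardless of trough (7.1). A level above 20 ng/mL leads to a 50% restart, which does lower 1.0 to 0.5 mg. These limit the harm, but none of them tells a site what to do at 1.0 mg with a trough between 10 and 20 ng/mL.

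**Conclusion.** The point holds and is minor. The footnote contradicts 3 of 12 printed doses read as always up, or 1 of 12 (Table 3 only) read as nearest with ties up. A 25% reduction ordered at 1.0 mg returns 1.0 mg on both readings. In the 50–70 kg row of Table 2, the second ordered reduction therefore leaves the daily dose unchanged, whichever interpretation is taken.

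A reader might go further and say that every row stalls at 1.0 mg, at the same step on both readings. That requires printed cells to apply across weight rows, which the documents do not state. If cells apply only to their own row and rounding is always up, five of the six rows stall at 1.5 mg.

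For troughs above 15 and below 20 ng/mL the ordered step is not wholly without effect, because the hold lowers the level for a time; only the reduction part is missing.

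Each discrepancy is one 0.5 mg tablet. The documents do not say how many participants would need two or more reductions. No sample size, power or analysis figure depends on this.

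**What to change.** Issue a clarification memo that states:

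1. The printed cells of Tables 2 and 3 govern wherever that dose occurs, at any weight. No two rows share an initial dose, so this never gives two answers.
2. All other steps round to the nearest 0.5 mg, ties up.
3. An ordered reduction may not leave the dose unchanged. At 1.0 mg or below, hold and contact the core team, which decides between 0.5 mg (where that is lower) and stopping.

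Align the web-page table if it differs. One gap needs a line of its own: under rule 2 an increase ordered at 0.5 mg (0.5 × 1.25 = 0.625) rounds back to 0.5 mg, so that case should also go to the core team.

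The cost is a memo and some core-team time. The trade-off is that 1.0 to 0.5 mg is a 50% cut and may take the trough below 5 ng/mL. The scheduled troughs should detect that, and it is why the step should be a team decision and not automatic.

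Dosing appears to be complete: SAP section 5.3 already counts 16 participants with the full 20 weeks of sirolimus, and SAP version 5.0 is dated 2019. If so, a note to file is enough. It should record the rounding actually used, list any ordered reductions that left the dose unchanged, and correct the algorithm before it is reused.

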5.2 Study Product Formulation and Preparation

Sirolimus tablets are obtained from Greenstone LLC. The inactive ingredients include sucrose, lactose, polyethylene glycol 8000, calcium sulfate, microcrystalline cellulose, pharmaceutical glaze, talc, titanium dioxide,

magnesium stearate, povidone, poloxamer 188, polyethylene glycol 20,000, glyceryl monooleate, carnauba wax, di-alpha tocopherol and other ingredients.

Sirolimus tablets 0.5 mg will be provided. These tablets also contain yellow iron (ferric) oxide and brown iron (ferric) oxide. They should be stored at 20° to 25°C [USP Controlled Room Temperature] (68° to 77°F). Dispense in a tight, light-resistant container as defined in the USP.

5.3 Pharmacy: Product Supply, Distribution, and Accountability

5.3.1 Study Product Acquisition/Distribution

Sirolimus will be available through the NIAID Clinical Research Products Management Center (CRPMC). The site pharmacist should obtain the study product(s) for this protocol by following the instructions in the manual *Pharmacy Guidelines and Instructions for DAIDS Clinical Trials Networks*.

Any study product not provided by the study must comply with the NIAID (DAIDS) policy that outlines the process for authorizing the use of study products not marketed in the US in NIAID (DAIDS)-supported and/or –sponsored clinical trials.

5.3.2 Study Product Accountability

The site pharmacist is required to maintain complete records of all study products received from the NIAID CRPMC and subsequently dispensed. All unused study products in US CRSs must be returned to the NIAID CRPMC (or as otherwise directed by the sponsor) after the study is completed or terminated. The procedures to be followed are in the manual *Pharmacy Guidelines and Instructions for DAIDS Clinical Trials Networks*.

5.4 Concomitant Medications

Whenever a concomitant medication or study agent is initiated or a dose changed, investigators must review the concomitant medication's and study agent's most recent package insert, Investigator's Brochure, or updated information from DAIDS to obtain the most current information on drug interactions, contraindications, and precautions.

Additional drug information may be found on the updated **ACTG Precautionary and Prohibited Medications** Database located at:
http://tprc.pharm.buffalo.edu/home/di_search/

5.4.1 Required Medications

Continuous ART, defined as active therapy with no treatment interruption longer than 7 consecutive days and a total duration off ART of no more than 7 days, is required through week 44. Changes in the regimen are allowed as long as a PI-based or cobicistat-boosted regimen is not initiated.

5.4.2 Prohibited Medications

These medications should be discontinued prior to study entry week 0 and are prohibited through week 32:

- Verapamil or diltiazem
- Protease inhibitors
- Medications known to be potent CYP3A inhibitors, (e.g., ritonavir, cobicistat, ketoconazole, or erythromycin)
- Anal or perianal administration of anti-HPV therapies (e.g., imiquimod, 5FU, veregen)
- Use of immunomodulators such as interleukins, interferons, and cyclosporin, HIV vaccine, systemic cytotoxic chemotherapy or investigational therapy
- Tacrolimus, mycophenolate mofetil, TNF-modulating medications, plaquenil or monoclonal antibodies targeting lymphocytes
- HPV vaccine
- Standard-of-care vaccines (e.g., pneumococcal polysaccharide or influenza vaccine within 14 days prior to study entry or 14 days prior to any post-entry study visit)

5.4.3 Precautionary Medications

A list of precautionary medications can be found on the A5337 PSWP.

6.0 CLINICAL AND LABORATORY EVALUATIONS

6.1 Schedule of Events

Evaluation	Screening	Entry	Sirolimus Initiation	Post-Entry Evaluations								Premature Treatment or Study Discontinuation	Confirmation of CD4 Decrease	Confirmation of Virologic Failure
	Week	0	12	13	14	16	20	24	32	44				
Days Post-Sirolimus Initiation			0	4	11	28	56	84	140	224				
Window	Within 60 days prior to entry		±1 week	±1 day (same days as PK)			±1 week (same days as PK)			±2 weeks				
Documentation of HIV	X													
Medical & Medication History	X	X												
Clinical Assessment	X	X	X	X	X	X	X	X	X	X	X			
Complete Physical Exam	X													
Targeted Physical Exam		X	X		X	X	X	X	X		X	X	X	
Hematology	X	X	X	X	X	X	X	X	X	X	X			
Liver Function Tests	X	X	X	X	X	X	X	X	X	X	X			
Blood Chemistry	X	X	X	X	X	X	X	X	X	X	X			
Calculated Creatinine Clearance	X	X	X	X	X	X	X	X	X	X	X			
Urinalysis	X		X		X	X	X							
Pregnancy Testing	X	X	X	if indicated										
Hepatitis Serology (see section 6.3.5)	X													
Assessment for Reactivation of Latent EBV	X						X	X	X	X	X			
CD4+/CD8+	X	X	X	X	X	X	X	X	X	X	X			

Evaluation	Screening	Entry	Sirolimus Initiation	Post-Entry Evaluations								Premature Treatment or Study Discontinuation	Confirmation of CD4 Decrease	Confirmation of Virologic Failure	
	Week	0	12	13	14	16	20	24	32	44					
Days Post-Sirolimus Initiation			0	4	11	28	56	84	140	224					
Window	Within 60 days prior to entry			±1 week	±1 day (same days as PK)			±1 week (same days as PK)			±2 weeks				
Cryopreserved PBMCs for HIV-1 Gag-specific CD8+ and CD4+ cell Immunity		X	X	X		X		X	X	X		X			
Stored Plasma for Inflammatory and Coagulation Markers		X	X	X		X		X	X	X		X			
Cryopreserved PBMCs for Markers of T-cell Activation and Proliferation		X	X	X		X		X	X	X		X			
Cryopreserved PBMCs for Exploratory Studies		X	X	X		X	X	X	X	X		X			
Stored Plasma for Antibody Quantitation		X	X	X				X	X	X		X			
Plasma HIV-1 RNA	X	X	X			X	X	X	X	X		X			X
HIV-1 Drug Resistance Genotyping (see section 6.3.7)															X
Cryopreserved PBMCs for Inducible RNA Assay			X					X	X	X					
Cryopreserved PBMCs for Cell-Associated RNA and DNA		X	X	X		X		X	X	X		X			
Stored Plasma for Residual Viremia by Single-Copy RNA Assay		X	X	X		X		X	X	X		X			
Stored Whole Blood for Gene Expression Assay			X	X		X		X	X	X					
Stored Plasma and PBMCs for Future Unspecified Testing		X	X	X		X		X	X	X		X			
Tuberculosis Test (see section 6.3.11)	X														
Chest Radiograph	X														
Anal Swabs/Anal Pap Test			X						X						
Oral Swabs		X	X	X		X		X	X	X		X			

6.1.1 Pharmacokinetic Evaluations

See section 6.3.12 for additional details.

Pharmacokinetic (PK) Sampling															
Evaluation	Weeks 12-16										Weeks 18-32				
	Week	12	13	13	14	14	15	15	16	16	18	20	24	28	32
	Day	0	4	7	11	14	18	21	25	28					
Window		±1 day (timed with other study visits as in section 6.1)										±1 week (timed with other study visits as in section 6.1)			
PK Whole Blood Samples for Trough Sirolimus Real-time Monitoring (see section 6.3.12)		X	X	X	X	X	X	X	X	X	X	X	X	X	
Stored Plasma for ARV PK (see section 6.3.12)	X	X		X					X	X		X	X	X	

6.2 Timing of Evaluations

6.2.1 Screening Evaluations

Screening evaluations must occur before any study medications, treatments or interventions.

Screening evaluations to determine eligibility must be completed within 60 days prior to study entry, unless otherwise specified.

In addition to data being collected on **participants** who enroll into the study, demographic, clinical, and laboratory data on screening failures will be captured in a Screening Failure Results form and entered into the ACTG database.

